Catheter ablation for treatment of atrial fibrillation/atrial flutter is a commonly performed procedure involving placement of 3 or 4 large (8-14 French) sheaths in the femoral vein. The procedure is performed on uninterrupted anticoagulation, which indicates that for warfarin and rivaroxaban the procedure is performed without holding any doses of anticoagulant medication. For apixaban, dabigatran and edoxaban, the procedure is performed with holding the dose of anticoagulant the night before the procedure and the morning of the procedure. The current standard of care is that at the conclusion of atrial fibrillation or atrial flutter ablation procedure, all venous sheaths are kept in place and the patient is transported to a recovery unit. Upon arrival in the recovery unit, the nursing staff will assess the ACT. Sheaths are not removed via manual compression until the ACT is < 165 seconds. During this time period, which may take several hours, the patients are lying flat on their back with their legs straight. Once the ACT is <165 seconds, the nurses will apply manual compression for 15 to 20 minutes. Following hemostasis, the patients lie flat with their legs straight for 3-4 hours. At that point, the access sites are rechecked to ensure hemostasis, and then the patient is allowed to ambulate.

In contrast, the patient receiving a vascular closure device (VCD) undergoes sheath removal at the conclusion of the procedure and hemostasis is achieved before the patient is removed from the table. When the patient is transported to recovery, they must lie flat on their back for 1 hour and then they are permitted to ambulate, irrespective of their ACT. Both patients receiving MC and VCD are monitored overnight for any post op complications such as recurrent bleeding, hematoma, pain or swelling from vascular access site.

Similarly, the Figure of 8 stitch has been used to achieve vascular closure following procedures involved access to the femoral vein, including leadless pacemaker implantation as well as catheter ablation of atrial fibrillation and atrial flutter. The process involves placing 0 silk suture through the skin and subcutaneous tissue below the lowest venous

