the patient's overall satisfaction with the recovery process. Each survey will be assigned a randomly generated confidential ID number and the data from the survey will be entered and analyzed into a spreadsheet that does not contain any patient identification information. A separate password protected spreadsheet will be maintained with an index of the randomly generated confidential ID numbers and the corresponding patient name and date of birth, however this will be stored separately and only the principal investigator will have access to this file. Once the survey data has been entered and confirmed, the original survey will be destroyed. A retrospective chart review of these patients would also be done to assess for any complications in the post procedure period, such as bleeding, hematoma formation, pseudo-aneurysm, arterio-venous fistula etc. Other parameters to be measured include the time to achieve hemostasis, time to ambulate and length of hospital stay. These parameters are all recorded in the patient's clinical record as part of the standard of care. All documentation related to the procedure will keep in a locked, secure file cabinet at St. Luke's Hospital and/or an encrypted, protected electronic storage device that can only be accessed by participating investigators.

B. Sample / Specimen Collection: N/A**C. Tissue Banking Considerations: N/A****D. Procedures to protect subject confidentiality:** All documentation related to the procedure will be kept in a locked, secure file cabinet at St. Luke's Hospital and/or encrypted, protected electronic storage device that can only be accessed by participating investigators.**E. Quality Assurance / Monitoring**

1. At the time of data collection, Drs. [name] and [name] will review the data together to ensure that it is entered correctly from the survey into the spreadsheet. Any discrepancy will be analyzed before the original paper form is discarded.

V. Data Analysis and Reporting**A. Statistical and Data Analysis:** Categorical variables will be compared with Chi-Square analysis. The patient factors that may contribute to the outcomes listed

below will be analyzed via logistic regression with subsequent multivariate logistic regression designed to compare these risk factors.

B. Outcome: The main outcomes of interest are

- Perception of pain during recovery process
- Overall satisfaction with recovery process
- Time to achieve hemostasis
- Time to ambulate following hemostasis

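### The ambulation clock in V.B starts at hemostasis, so it leaves out the time manual-compression patients lie flat waiting for their ACT to fall

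*Combined protocol and SAP*

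**What the plan says.** Section V.B (Outcome) lists "Time to ambulate following hemostasis" and, as a separate item, time to achieve hemostasis. The paragraph after the list expects both to be shorter with the VCD. Sections II.E and IV.A also name "time to achieve hemostasis" and say the listed times are in the clinical record. No section says when the hemostasis clock starts.

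The ambulation outcome is not worded consistently. I.A and I.C call it time to ambulation, and II.E and IV.A time to ambulate, with no start point. Only V.B ties it to hemostasis.

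Section I.B (Background and Significance) describes the care paths:

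- **MC:** the patient goes to recovery with all sheaths in place. An ACT rule governs their removal: "Sheaths are not removed via manual compression until the ACT is < 165 seconds". The text then gives the length of this wait and the patient's position: "During this time period, which may take several hours, the patients are lying flat on their back with their legs straight". After that "the nurses will apply manual compression for 15 to 20 minutes". A further period of bed rest is described: "Following hemostasis, the patients lie flat with their legs straight for 3-4 hours". The groin is checked again, "and then the patient is allowed to ambulate".
- **VCD:** the patient "undergoes sheath removal at the conclusion of the procedure" and has hemostasis before leaving the table. After transport to recovery there is 1 hour flat, then permission to walk whatever the ACT.
- **Figure-of-8 stitch (F08S):** protamine, sheath removal, tying of the suture and 5 minutes of groin pressure. No bed-rest time and no ACT rule are given.

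I.B also says that MC and VCD patients are both monitored overnight.

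**The concern.** A comparison of times between groups needs a start point that the groups share. Hemostasis is not one. In the MC path it comes after the ACT wait and the compression; in the VCD path it comes at the end of the procedure. Starting the clock there removes from the MC group an immobile period that the VCD group does not have.

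I.B names earlier ambulation as an open question, and I.A and I.C name time to ambulation as an outcome of interest. As V.B defines it, the outcome answers a narrower question: how long bed rest lasts once bleeding has stopped. It does not say how long after the ablation the patient could walk.

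The undefined origin of time to hemostasis adds to this. If the person reading the chart starts that clock at sheath removal or at the start of compression, the wait appears in neither of these two outcomes.

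**Working it through.** The plan gives no figure of its own to reproduce: II.C has no power calculation, and no ambulation time is targeted. The check is arithmetic on the I.B timeline.

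**Inputs**

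- *w*: end of ablation to MC sheath removal. I.B says only that it may take several hours. **Assumed** 0 to 5 h.
- *c*: MC compression, 15-20 min = 0.25-0.33 h (I.B).
- *b*: MC flat time after hemostasis, 3-4 h (I.B).
- VCD flat time, about 1 h (I.B).
- Simplifications: MC hemostasis is taken as the end of compression; VCD closure and transport times are ignored at first.

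**Formulas for the MC-VCD gap in permitted ambulation**

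- As V.B defines it: *b* − 1 = 3 − 1 to 4 − 1 = **2-3 h**, whatever *w* is.
- From end of ablation: *w* + *c* + *b* − 1 = *w* + 2.25 to *w* + 3.33 h.
- Omitted by the ambulation outcome alone: *w* + *c*, that is, the wait plus 15-20 minutes.
- Omitted by both hemostasis and ambulation times, if hemostasis is timed from sheath removal: *w*. As a share of the whole gap: *w* / (*w* + *c* + *b* − 1).
- Omitted by both, if hemostasis is timed from end of ablation: 0.

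| Assumed *w* | Gap from end of ablation | Gap as V.B defines it | Omitted by ambulation outcome | Share omitted by both times (sheath-removal origin) |
|---|---|---|---|---|
| 0 h | 2.25-3.33 h | 2-3 h | 0.25-0.33 h | 0% |
| 1 h | 3.25-4.33 h | 2-3 h | 1.25-1.33 h | 1/4.33 to 1/3.25 = 23-31% |
| 3 h | 5.25-6.33 h | 2-3 h | 3.25-3.33 h | 3/6.33 to 3/5.25 = 47-57% |
| 5 h | 7.25-8.33 h | 2-3 h | 5.25-5.33 h | 5/8.33 to 5/7.25 = 60-69% |

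**Sensitivity.** The VCD hour starts in recovery, not at hemostasis. If VCD closure plus transport takes an assumed 0.5 h, the post-hemostasis gap could fall to 1.5-2.5 h and the whole gap to *w* + 1.75 to *w* + 2.83 h. The shares for *w* = 1 to 5 h then run from 1/3.83 = 26% to 5/6.75 = 74%. Any delay before VCD sheath removal would also come off the omitted hours. The omission is therefore approximately the wait.

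**Direction.** Every omitted term lengthens the MC path, so the omission shrinks the MC-VCD difference.

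**F08S.** With no bed-rest time or ACT rule stated, its contrasts cannot be sized.

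**The case against.** The two V.B outcomes are listed one after the other and can be read as consecutive segments of one timeline, with the first covering everything up to hemostasis. I.B describes both MC and VCD care from the end of the procedure. With that origin the wait falls in time to hemostasis, and nothing is lost across the pair. This stands as a possible reading, but no section states it, and the ambulation outcome taken alone still omits the wait.

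A reader might infer that the wait is certainly in neither time. The documents do not support that, because no section adopts a sheath-removal origin either. A reader might also infer that no listed duration covers the wait. Length of hospital stay does span it. With MC and VCD patients both kept overnight, though, it is unlikely to reveal a difference of a few hours. Pain and satisfaction may reflect the wait but do not measure it.

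The unanchored wording in I.A, I.C, II.E and IV.A leaves room for the total interval. That is a reason to reconcile it with V.B, since the two wordings can give different quantities.

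It is also fair that the consequence is limited. The hypothesis in I.A and the objective in II.A concern satisfaction and complications, no sample size depends on these times, and the stated bed-rest times alone still separate MC from VCD by about 2-3 h.

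**Conclusion.** The point holds. By its own wording, the V.B ambulation outcome omits the MC wait and shows only about 2-3 h of the MC-VCD difference in permitted ambulation. The difference from end of ablation is understated by approximately the length of the wait.

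Only the 2-3 h comes from the documents. The larger figures rest on an assumed wait of 0 to 5 h. They also describe permission to walk under the stated routines; actual walking may come later in either group. To say that the understatement equals the wait exactly would be too strong, because compression, transport and VCD closure time also enter.

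Nor do the documents support reading this as a bias in favor of the VCD. It hides part of a VCD advantage and creates no false one.

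Whether time to hemostasis recovers the wait is open, because its origin is not stated. This is a worthwhile and cheap improvement to an outcome definition. It does not threaten the registry's main comparison.

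**What to change.** In V.B, define time to hemostasis and time to ambulation from one common origin in all three groups: end of ablation, before any sheath removal or closure step. Keep hemostasis-to-ambulation as a secondary component, since it describes bed rest after closure. Use the same terms in I.A, I.C, II.E, IV.A and the expected-results paragraph of V.B.

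The cost is revised wording and one extra chart time per patient, for about 120 expected patients. Two things need checking. II.E and IV.A say the listed parameters are charted but not whether as durations or clock times, so the availability of an end-of-ablation time must be confirmed. A charted procedure-end time could also fall after on-table closure, so each record's origin must be shown to precede it. Nothing more is asked of patients, and care does not change.

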A. If you answered yes, and if you had a closure device used for this procedure, would you prefer this method over manual compression:

Yes	No
-----	----

5. Please rate your level of concern for having a bleeding event after the procedure, are you:

Extremely concerned	Very concerned	Concerned	Slightly concerned	Not concerned
---------------------	----------------	-----------	--------------------	---------------

6. Would you have been comfortable being discharged home, about 4 hours after you were allowed to sit up, on the same day as your ablation?

Yes	No
-----	----

7. Please write any additional comments regarding your post-procedure recovery below:

Thank you for your participation in this survey.
